9.2.	Measurement Methods	18
9.3.	Measurement Time Points	18
10.	STATISTICAL CONSIDERATIONS	18
10.1.	Statistical Design	18
10.2.	Descriptive Statistics and Exploratory Data Analysis	18
10.3.	Primary Analysis	19
10.3.1.	Analysis Population	19
10.3.2.	Analysis Plan	19
10.4.	Secondary Analysis	19
10.4.1.	Analysis Population	19
10.4.2.	Analysis Plan	19
10.5.	Sample Size	19
10.6.	Accrual estimates	19
10.7.	Criteria for future studies	19
11.	REFERENCES	20
Appendix A		21
Appendix B		23

PROTOCOL SYNOPSIS

TITLE	A Phase 2 Study of ¹⁸ F-FTC-146 PET/CT in Patients with Newly-Diagnosed Osteosarcoma
STUDY PHASE	Phase 2
INDICATION	Tumor imaging
INVESTIGATIONAL PRODUCT	¹⁸ F-FTC-146
PRIMARY OBJECTIVE(S)	Demonstrate correlation of pre-post reduction in ¹⁸ F-FTC-146 PET/CT with amount of post-treatment tumor necrosis in newly-diagnosed and treated osteosarcoma patients.
SECONDARY OBJECTIVE(S)	Demonstrate correlation of pre-post reduction in ¹⁸ F-FTC-146 PET/CT with amount of post-treatment pain reduction in newly-diagnosed and treated osteosarcoma patients.
TREATMENT SUMMARY	Participants will be assessed with ¹⁸ F-FTC-146 PET/CT imaging at baseline and after neoadjuvant (pre-surgery) chemotherapy but before surgery itself.
SAMPLE SIZE	5
STATISTICAL CONSIDERATIONS	
Descriptive statistics and correlations will be calculated. Means, medians, and standard deviations of:
 
 1. Histologically determined percentage of necrosis in post-chemotherapy resected tumor. 2. Pre- and post-treatment SUVmax in tumor ROI, and the pre-post percent change. 3. Pre- and post-treatment pain score, and the pre-post difference. 
Primary Analysis
 
 1. The following will be recorded for each patient 
 (a) the histological percentage of necrosis and (b) the percent reduction in SUVmax. 2. The histological percent necrosis will be plotted against SUVmax percent reduction to calculate rank correlation. 
Secondary Analysis
 
 1. The following will be recorded for each patient 
 (a) the post-treatment reduction in pain score (b) the percent reduction in SUVmax 2. The reduction in pain score will be plotted against SUVmax reduction to calculate rank correlation. 
Sample Size
 
Preliminary approval for this study is for 5 subjects only. An eventual sample size of 20 will provide 90% power at one-sided 5% error to detect a correlation as low as 0.60.

SCHEMA

LIST OF ABBREVIATIONS AND DEFINITION OF TERMS (Example)

CBC	Complete blood count
CI	Confidence interval
C _{MAX}	Maximum concentration of drug
CNS	Central nervous system
CRF	Case report/Record form
CR	Complete response
CSM	Conventional Staging Method
CTCAE	Common Terminology Criteria for Adverse Events
DLT	Dose Limiting Toxicity
DSMB	Data Safety Monitoring Board
ECG	Electrocardiogram
ECOG Performance Status	Easter Cooperative Oncology Group Performance Status
EFS	Event Free Survival
FDG	Fluorodeoxyglucose
GI	Gastrointestinal
Hgb	Hemoglobin
HIV	Human Immunodeficiency Virus
HPF	High-power field
HTN	Hypertensions
IPI	International Prognostic Index
IRB	Institutional Review Board
IV	Intravenous
LLN	Lower limit of normal
NHL	Non-Hodgkin's Lymphoma
NPV	Negative Predictive Value
OS	Overall survival
PET/CT	Positron emission tomography – computed tomography
PLT	Platelet
PD	Progressive diseased
PPV	Positive Predictive Value
PFS	Progression free survival
PR	Partial response
QD	Once daily
RECIST	Response evaluation criteria in solid tumors
RM	Residual Mass

ROC	Receiver-Operative-Characteristic
RR	Response rate
S1R	Sigma-1 receptor
SAE	Serious adverse event
SD	Stable disease
SUV	Standard Uptake Value
TTP	Time to progression
ULN	Upper limit of normal
UNK	Unknown
WBC	White blood cell
WHO	World Health Organization

1. OBJECTIVES

1.1. Primary Objective

Demonstrate correlation of pre-post reduction in ^{18}F -FTC-146 PET/CT with amount of post-treatment tumor necrosis in newly-diagnosed and treated osteosarcoma patients.

1.2. Secondary Objective

Demonstrate correlation of pre-post reduction in ^{18}F -FTC-146 PET/CT with amount of post-treatment pain reduction in newly-diagnosed and treated osteosarcoma patients.

2. BACKGROUND

2.1. Study Disease

Osteosarcomas are the most common bone sarcomas in adults. Patients with localized disease are curable with neoadjuvant chemotherapy followed by surgical resection. The single most important prognostic factor is the percent necrosis in the post-chemotherapy resected specimen. Patients with tumors > 90% necrosis have an excellent long-term survivals. However, patients with < 90% necrosis have a poor prognosis with early signs of disease recurrence with metastatic spread.

2.2. Study Agent/Device/Imaging Procedure

[name], has developed a novel sigma-1 receptor (S1R) imaging probe, ^{18}F -FTC-146, that is highly-selective for targeting S1R expressed in brain. S1Rs are widely distributed throughout the brain where they interact with ion channels and neurotransmitters involved in learning, memory, and the development of compulsive behavior. The proposed research is technically innovative because of its use of ^{18}F -FTC-146, the only known tracer that does not suffer from off-target binding and *in vivo* instability, for S1Rs. The S1R targeting specificity of ^{18}F -FTC-146 has already been studied in rodents, monkeys, and more recently in humans. With the departmental support provided by [name] [name] (Chair, Department of Radiology), [name], in collaboration [name] [name], first obtained an Exploratory Investigational New Drug Application (IND 126459) to use ^{18}F -FTC-146 in first-in-human studies, and have previously converted the exploratory IND to a full IND (IND [REDACTED]).

Since [name] has shown that ^{18}F -FTC-146 has excellent affinity to S1R (> 100,000-fold higher than any other receptor targets in the brain including S2R) and the lipophilicity of this ligand ($\log D_{\text{pbs}7.4} = 1.45$) falls in an ideal range for the Blood Brain Barrier, these favorable properties allow ^{18}F -FTC-146 to be a promising candidate for selective PET S1R-neuroimaging. He has made ^{18}F -FTC-146 and knows its biodistribution and pharmacokinetics in mice. The radiotracer displays good distribution volume (~2.4) and excellent S1R-specificity and selectivity in WT vs S1R knockout (KO) mice. S1R expression level strongly correlated with ^{18}F -FTC-146 autoradiography signal in brain regions with high S1R expression when compared with immunohistochemical staining. To determine

test-retest variability of brain uptake (%ID/g), 3 healthy mice were injected with ^{18}F -FTC-146 with a 7-day interval between measurements, and results ranged from 10 to 17% in 10 brain regions. In rat biodistribution studies, ^{18}F -FTC-146 demonstrated specific uptake in S1R rich rat organs, including the lungs, pancreas, spleen, and brain. Preliminary monkey PET/MRI studies revealed similar ^{18}F -FTC-146 accumulation in brain (mainly in cortical structures, cerebellum, and vermis) that could be attenuated by pretreatment with S1R agonist haloperidol. In addition, he also performed supporting dosimetry and toxicity studies in rodents for clinical translation. An Exploratory Investigational New Drug (eIND) Application for ^{18}F -FTC-146 was submitted to the Food and Drug Administration (FDA) for first-in-human studies to examine radiotracer biodistribution and pharmacokinetics and first-in-human studies in typically developing volunteers (N = 10) and patients with pain (N = 30) were performed by his group. His initial evaluation of ^{18}F -FTC-146 in humans shows that this radiotracer is safe and the adsorbed radiation doses measured are acceptable to be used for other indications including OCD, HD, and other neurodegenerative diseases. More recently, eIND 126459 was converted to full IND [REDACTED] (activated 9 May 2018).

2.3. Clinicaltrials.gov

This study of ^{18}F -FTC-146 for PET/CT imaging is investigational, and has been submitted to IND [REDACTED].

This study is registered on ClinicalTrials.gov as NCT04365660.

2.3.1. Clinicaltrials.gov Outcomes

2.3.1.1 Primary Outcome (Outcome 1)

Title: Detection of tumor necrosis post-chemotherapy

Description: Participants will be assessed with ^{18}F -FTC-146 PET/CT imaging at baseline and after neoadjuvant (pre-surgery) chemotherapy but before surgery itself. Chemotherapy will be nominally three 3-week cycles administered over up to 12 weeks. The ability of ^{18}F -FTC-146 PET/CT to evaluate treatment effect will be assessed as the percentage of tumor that is assessed as necrotic after the treatment course. The outcome will be reported as the mean percentage of the resected tumor (removed by surgery) that is assessed by histopathology as necrotic, with standard deviation.

Timeframe: 12 weeks

2.3.1.2 Secondary Outcomes

Outcome 2

Title: Maximum Standardized Uptake Value (SUVmax)

Description: Participants will be assessed with ^{18}F -FTC-146 PET/CT imaging at baseline and after neoadjuvant (pre-surgery) chemotherapy but before surgery itself. Chemotherapy will be nominally three 3-week cycles administered over up to 12 weeks. Based on the PET/CT scans, the maximum standardized uptake value (SUVmax) in the tumor region of interest (ROI) will be calculated at baseline and after treatment. The outcome will be reported as the mean percent change in SUVmax from baseline to post-treatment, with standard deviation.

Timeframe: 12 weeks

Outcome 3

Title: Use of PROMIS (Patient-Reported Outcomes Measurement Information System) to Assess Treatment Effect

Description: Participants will receive neoadjuvant (pre-surgery) chemotherapy, nominally three 3-week cycles administered over up to 12 weeks. The treatment effect of the neoadjuvant chemotherapy will be assessed as the change in scores on the PROMIS (Patient-Reported Outcomes Measurement Information System) questionnaire, from baseline to post-treatment. The result will be reported as the mean difference from baseline to post-treatment, with standard deviation.

Timeframe: 12 weeks

2.4. Rationale

Currently, there is no accurate imaging modality evaluating the amount of necrosis in the tumor after neoadjuvant chemotherapy. This study will evaluate the amount of tracer uptake in osteosarcoma tumors prior to chemotherapy and after neoadjuvant chemotherapy. We would also like to see if the uptake correlates with pain. This is a feasibility study, but we will try to correlate the amount of tracer uptake with the amount of necrosis in this small patient population. If there is correlation, we will proceed with a larger study to confirm the results.

2.5. Preliminary results

The pre-clinical information below is from a personal communication with [name], DVM, MS, DACVIM (Oncology); Assistant Professor of Oncology, College of Veterinary Medicine at the University of Missouri.

Current evidence for pain/gait outcomes in canine osteosarcoma is described by relatively few studies. Subjective owner questionnaires, force plate analysis, and serum biomarkers

have been utilized to assess response. His group hypothesized that intervention would cause objective evidence of pain control when evaluating S1R activity in canine tumors. Evaluations of 3 dogs with primary bone cancer included ^{18}F -FTC-146 PET/CT scans, gait and kinematic motion analysis, validated owner questionnaires (CBPI), and serum N-telopeptide (NTx) concentration. Dogs received baseline staging; ^{18}F -FTC-146 PET prior to treatment and on Day 28; and Day 0; 7; 14; and 28 CBPI; serum banking for NTx; orthopedic exam; and gait analysis. Each dog received a different treatment: Dog 1 received radiation and zoledronate; Dog 2 received single agent zoledronate; and Dog 3 had an amputation. Dog 1 had a 50% decrease in S1R activity on its day 28 PET scan. Dog 2 had a 25% decrease in activity. Dog 3 will have its second scan in the next few weeks. Both dogs finishing their treatment have had improvement in subjective pain assessment. Data analysis of their CBPI, NTx, and force plate stance are underway.

2.6. Study Design

This is an open-label, single-arm phase 2 study to evaluate ^{18}F -FTC-146 PET/CT in newly-diagnosed osteosarcoma patients.

3. PARTICIPANT SELECTION AND ENROLLMENT PROCEDURES

3.1. Inclusion Criteria

- 3.1.1 Patients with biopsy-proven osteosarcoma requiring local surgical intervention
- 3.1.2 Age \geq 18 years
- 3.1.3 ECOG \leq 2
- 3.1.4 Ability to understand and the willingness to sign a written informed consent document

3.2. Exclusion Criteria

- 3.2.1 Chemotherapy in the past 2 months
- 3.2.2 Prior history of allergic reaction to ^{18}F -FTC-146
- 3.2.3 Pregnant or nursing

3.3. Informed Consent Process

All participants must be provided a consent form describing the study with sufficient information for participants to make an informed decision regarding their participation. Participants must sign the IRB approved informed consent prior to participation in any study specific procedure. The participant must receive a copy of the signed and dated consent document. The original signed copy of the consent document must be retained in the medical record or research file.

3.4. Study Timeline

3.4.1. Primary Completion:

Primary completion is the date that the final datum is obtained/expected to be obtained for the primary outcome. The timeframe for primary completion for an individual subject

is approximately 3 to 4 months from time of consent. This datum is expected to be obtained approximately 12 months from the time the study opens to accrual.

3.4.2. Study Completion:

The study is expected to reach overall completion (last datum from last subject) approximately 18 months from the time the study opens to accrual.

4. IMAGING AGENT/DEVICE/PROCEDURE INFORMATION

4.1. Treatment / Procedure Plan

This is a phase 2 study of ¹⁸F-FTC-146 PET/CT in patients with newly-diagnosed osteosarcoma. The study will be conducted at Stanford University.

This study will be conducted over the period in which subjects receive 3 cycles of neoadjuvant chemotherapy, which is standard of care. This time period may vary from subject to subject. Each participant will be individually told how long their chemotherapy will take.

It is anticipated that this study will require approximately 3 days of active participation from each study subject and will involve:

- Screening assessments,
- Two ¹⁸F-FTC-146 PET/CT scans
- Two PROMIS Questionnaires surveys, ie, Quality of Life (QoL) surveys (Appendix B)

Participants must sign the IRB-approved consent form prior to participation in any study-specific procedure.

Screening: Screening assessments must occur within 28 days prior to start of treatment.

Screening tests, examinations, or procedures include:

- Demographics: Date of birth, sex, ethnicity.
- Medical history: Review of medical history, including surgery and cancer history, other cancer treatments subject has received, current and past medicines subject is taking or has taken, and reproductive status.
- Performance status: Subject will be asked about their ability to perform everyday tasks.
- β -HCG (pregnancy test): β -HCG must be done within 7 days of first scan. Subjects who are currently pregnant or breast-feeding may not participate in this study. It is not known whether ¹⁸F-FTC-146 is safe for the fetus (unborn child) or a breast-fed baby.

Enrollment:

Subjects may be enrolled into the study if they meet all eligibility requirements.

Study Procedures:

- **2 PET/CT Scans**
- **2 PROMIS QoL surveys**

The ^{18}F -FTC-146 PET/CT scans and QoL surveys will occur before subjects start chemotherapy and the final study visit will occur after subjects have completed chemotherapy. It is anticipated that the entire research study will take approximately 1 year.

PET/CT: All subjects in this study will receive 2 PET/CT scans using the experimental investigational radiotracer ^{18}F -FTC-146. After receiving an ^{18}F -FTC-146 PET/CT scan at baseline, subjects will receive 3 cycles of neoadjuvant chemotherapy as determined by their oncologist. This treatment is part of subject's regular medical care. At the final study visit, after completing the 3 cycles of neoadjuvant chemotherapy, subjects will have a 2nd PET-CT scan.

PROMIS Questionnaires: At the baseline Study Visit (before first scan) and Final Study Visit (before second scan), subjects will be asked to complete questionnaires about pain intensity and pain interference with their life.

Completion of participation:

Patient's participation in the study is complete 30 days after the final investigational scan, once the PROMIS questionnaire and pathology report have been collected.

4.2. PET/CT Scan

- **Radionuclide or imaging agent and chemical form:** ^{18}F -FTC-146
- **Number of radioisotope / imaging agent administrations; route of administration; and administered activity in mCi):** For PET scans, each subject will receive a manual, injection of 10 mCi +/- 20% ^{18}F -FTC-146 intravenously; this is usually through a peripheral IV line in the extremities, and may also be through a peripherally inserted central catheter (PICC line), a Port-A-Cath, or Hickman catheter. These participants will be administered twice with ^{18}F -FTC-146, once at baseline (pre-chemotherapy) and once at final study visit (post chemotherapy).

- **Dosimetry information:**

We estimate that the amount of radiation exposure is about 19.2 mSv, which is approximately equal to 38% of the limit that radiation workers (for example, a hospital x-ray technician) are allowed to receive in one year. (Hjørnevik, *et al*, 2017)

An Exploratory Investigational New Drug (eIND) Application for ^{18}F -FTC-146 (IND [REDACTED]) was approved by the Food and Drug Administration (FDA) for first-in-human studies to examine radiotracer biodistribution and pharmacokinetics and first-in-human studies in typically developing volunteers (N = 10) and patients with pain (N = 15) [see reference below] were performed by our group. (Cipriano, *et al*, 2018; Shen B, *et al*, 2017; Hjørnevik, *et al*, 2017)

Our initial evaluation of ^{18}F -FTC-146 in humans provided evidence that this radiotracer is safe and the adsorbed radiation doses measured are acceptable to be used for other indications including OCD, HD, and other neurodegenerative diseases.

(Cipriano, *et al*, 2018; Shen B, *et al*, 2017; Hjørnevik, *et al*, 2017) In May 2018, eIND 126459 was successfully converted to the full IND 136678.

- **Source of the study agent:** ^{18}F -FTC-146 will be prepared under aseptic conditions and its quality assessed in the MIPS Cyclotron and Radiochemistry Facility within the Division of Nuclear Medicine and Molecular Imaging at Stanford Hospital and Clinics.
- **Agent ordering:** The agent will be requested by a member of the study team, and prior to radiopharmaceutical administration, use of ^{18}F -FTC-146 will be approved and prescribed by a study investigator or sub-investigator.
- **Radionuclide / imaging agent management, control, and security :** A member of the research team trained in radiation safety will securely transport the dose of ^{18}F -FTC-146 to the PET/CT suite in the Stanford Nuclear Medicine for imaging. The nuclear medicine technologist will follow radiation safety procedures when checking in the package.
- **Scan description (for well-established imaging procedures):** A low-dose CT will be obtained from vertex to toes; this will use 120 kV and dose modulation based on body habitus, ranging 10 to 105 mA. This will be followed by 30 to 60-minute limited dynamic PET emission scan in a region of interest of known osteosarcoma (a 30-minute scan will be obtained for most patients; this may be extended for up to 60 minutes in 1 to 2 patients). Immediately after the limited dynamic scan, a static whole-body PET emission scan will be acquired (approximately 25 minutes).
- **Number of scans to be performed on a single research subject:** Each subject will receive 2 PET/CT scans.
- **For each imaging procedure provide the setup and technique sufficient to permit research subject radiation dose modeling:** The chief technologist can usually provide this information. Set up will be according to standard institutional practice for whole body PET/CT scans.

5. STUDY PROCEDURES

5.1. Criteria for Removal from Study

Subjects will be removed from the study if there is withdrawal of consent, non-compliance, or if the subject is female and has become pregnant.

5.2 Alternatives

The alternative is to not be on this study and receive standard of care treatment.

6. STUDY CALENDAR

	Screening ^b	Baseline (Pre-chemo)	Final Visit ^e
Investigational Scan ^a		X	X
Informed consent	X		
Demographics	X		
Medical history	X		
Height		X	
Weight		X	
Performance status	X		
β-HCG	X		
PROMIS Questionnaires		X ^c	X ^c
Adverse event evaluation ^d		X	X
Pathology report			X ^e

- a Patients will receive neoadjuvant chemotherapy, which is standard of care. It is not part of this protocol. Neoadjuvant chemotherapy will start after baseline investigational scan. The second investigational scan will occur after neoadjuvant chemotherapy.
- b Screening: Screening period is 28 days. β-HCG must be done within 7 days of first scan.
- c Patients will complete PROMIS questionnaires at Baseline (before 1st scan) and at Week 9 (before 2nd scan). Questionnaire may be completed within 2 weeks prior to each investigational scan.
- d Adverse events: Adverse events will be recorded from the time of the first investigational scan and for 30 days from the time of the final investigational scan. **Only AEs related to PET/CT procedure will be collected and recorded.**
- e Patient's participation in the study is complete 30 days after the final investigational scan, once the PROMIS questionnaire and pathology report have been collected.

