7. ADVERSE EVENTS AND REPORTING PROCEDURES

7.1. Potential Adverse Events

The patients will be injected with ¹⁸F-FTC-146, which is an investigational drug. An IND application has previously been filed with FDA (IND ████████ IND-holder [name]). Toxicity studies performed by unbiased party have shown no treatment related toxicity at 3 and 15 days after treatment with a single dose (250-fold the expected clinical dose) in a single rodent species. There are no known pharmacological risks of the drug. However, there is risk of radiation dose as described below.

This research study involves exposure to radiation from two 10 mCi +/- 20% doses of ¹⁸F-FTC-146. The radiation exposure from two 10 mCi +/- 20% doses of ¹⁸F-FTC-146 is

maximally 19.2 mSv, which is approximately equal to 38% of the limit that radiation workers (for example, a hospital X-ray technician) are allowed to receive in 1 year. This amount of radiation involves minimal risk and is necessary to obtain the research information desired.

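### No pregnancy test is scheduled before the second ¹⁸F-FTC-146 dose, when the only scheduled β-HCG result would be about 63 to 91 days old

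*Combined protocol and SAP*

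**What the plan says.** In the Section 6 calendar, the β-HCG row has a single mark, under Screening, and nothing under Baseline or Final Visit. Footnote b states that the test "must be done within 7 days of first scan". Section 4.1 repeats the rule in its list of screening assessments. The medical history in Section 4.1 covers past and current medicines the participant is "taking or has taken, and reproductive status", but the calendar marks medical history only under Screening too.

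Section 4.2 has the tracer given twice, "once at baseline (pre-chemotherapy) and once at final study visit (post chemotherapy"), and its scan description includes a low-dose CT of the whole body. On the interval between scans, Section 2.3.1.1 says: "Chemotherapy will be nominally three 3-week cycles administered over up to 12 weeks". Footnote c of the calendar places the second questionnaire "at Week 9 (before 2nd scan"). Section 4.1 adds that the length of the chemotherapy period can differ between participants.

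On pregnancy itself, Section 3.2.3 excludes pregnant or nursing patients. Section 4.1 says it is not known whether the tracer "is safe for the fetus (unborn child) or a breast-fed baby". Section 5.1 removes a participant for withdrawn consent, for non-compliance, "or if the subject is female and has become pregnant".

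**The concern.** The protocol treats pregnancy as a bar to tracer exposure and sets a 7-day limit on the age of the test before the first scan. It gives no reason to drop that limit for a second administration of the same tracer at the same activity. Per-scan timing was clearly workable, because footnote c sets a window for the questionnaires before each of the two scans. The safety test has no matching rule.

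What is at stake is patient safety. A site could follow the schedule exactly and give the second research dose and CT with no current pregnancy result. A pregnancy that began during chemotherapy would then depend on the participant or the treating team to bring it to light. The eligibility criteria contain no contraception requirement that would make this less likely.

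**Working it through.** **Inputs**
- Age of the test at the first scan: 0 to 7 days (Section 6 footnote b; Section 4.1), taking the test to precede the scan.
- Length of chemotherapy: nominally three 3-week cycles, up to 12 weeks (Section 2.3.1.1).
- Exposure from the two tracer doses together: "maximally 19.2 mSv, which is approximately equal to 38% of the limit" for radiation workers (Section 7.1).
- Approved size: 5 participants (Section 10.5).

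**Assumptions.** Chemotherapy starts right after the first scan, and the second scan follows right after the third cycle. The documents give the order of these events but cap neither gap.

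**The plan's own figure.** 3 cycles × 3 weeks = 9 weeks, which reproduces the Week 9 timing in footnote c. 9 × 7 = 63 days. The upper length is 12 × 7 = 84 days.

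**Age of the last scheduled β-HCG at the second dose** = days from test to first scan + days between scans.

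| Test to first scan | 9 weeks between scans | 12 weeks between scans |
|---|---|---|
| 0 days | 0 + 63 = 63 days | 0 + 84 = 84 days |
| 7 days | 7 + 63 = 70 days | 7 + 84 = 91 days |

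Against the 7-day limit for the first scan, the extremes are 63 / 7 = 9 times and 91 / 7 = 13 times. Any delay at either end adds to these ages, so 91 days is not a hard maximum.

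**Exposure at the second dose.** If the two doses are equal, 19.2 / 2 = 9.6 mSv at most. This is the participant's dose from the tracer. The documents give no fetal dose and no separate CT dose.

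**Participants affected.** Only those able to become pregnant. The documents do not give their number, so at the approved size it lies between 0 and 5.

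**With a second test.** If β-HCG were also required within 7 days before the second scan, the newest result at that dose would be 0 to 7 days old.

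**The case against.** The protocol does not ignore pregnancy after screening. Section 5.1 already removes a participant known to be pregnant, and Section 4.2 requires an investigator or sub-investigator to approve and prescribe the tracer before it is given, so a physician decision precedes the second dose. Chemotherapy and surgery are standard care outside the protocol, and pregnancy testing may take place there. The consent pages were not available and could contain contraception advice, a duty to report pregnancy, or a question before each scan. The affected number may be zero, and neither the age of the test nor the 9.6 mSv figure measures harm to a fetus.

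Part of this stands. A known pregnancy already stops the second dose, so the gap is one of detection. The ratio to the 7-day limit and the per-dose exposure describe the gap and do not estimate risk. The unseen consent pages limit the finding to the calendar and Section 4.1.

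The rest does not close the gap. Section 5.1 states a consequence without a means of finding the pregnancy. The approval step in Section 4.2 names no pregnancy check. Testing in standard care may happen, but the protocol neither requires nor relies on it, and the same care setting did not stop the protocol from requiring its own test before the first scan.

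**Conclusion.** The concern holds. As written, the schedule permits a second research tracer dose and CT when the only scheduled pregnancy result is about 63 to 91 days old. That range rests on no gap between scan and chemotherapy at either end, a test 0 to 7 days before the first scan, and 9 to 12 weeks of chemotherapy. Confidence is high on what the calendar and Section 4.1 schedule. How often a pregnancy would be missed cannot be estimated from the documents. The chance is probably small in a study of 5, but the potential harm is serious and the remedy is cheap, so the change should be made. It has no bearing on the correlations, the sample size or the analysis populations.

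**What to change.** Amend footnote b and the screening text in Section 4.1 so that, for participants able to become pregnant, β-HCG is done within 7 days before each investigational scan. Add a β-HCG mark in the Final Visit column. State that a positive result means the second dose is withheld and Section 5.1 applies; this last sentence makes explicit what the removal rule already implies.

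The cost is a small amendment in three places and one extra routine test per affected participant, done around a visit that is already planned. No statistical figure changes.

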9.3. Measurement Time Points

1. Imaging and pain measurements will be made just before and after treatment (3 cycles of chemotherapy).
2. Tumor histology will be measured on the post-chemotherapy resected tumor, after the second PET/CT scan.

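### The study calendar times the second pain questionnaire at Week 9, which fits only a nominal 9-week course; in a longer course, followed literally, it gives a pain score taken during treatment

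*Combined protocol and SAP*

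**What the plan says.** The second pain form is timed in several places, and the rules differ.

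- **Section 6, footnote c, first sentence:** "Patients will complete PROMIS questionnaires at Baseline (before 1st scan) and at Week 9 (before 2nd scan". This is the only place that gives the second form a week number.
- **Section 6, footnote c, next sentence:** "Questionnaire may be completed within 2 weeks prior to each investigational scan". This rule counts back from the scan.
- **Section 6, table:** the second questionnaire sits in the Final Visit column, together with the second scan.
- **Section 6, footnote a:** "The second investigational scan will occur after neoadjuvant chemotherapy". No week is given for the scan.
- **Section 4.1, PROMIS paragraph:** the forms are due "At the baseline Study Visit (before first scan) and Final Study Visit (before second scan", again without a week number.
- **Section 9.3:** "Imaging and pain measurements will be made just before and after treatment (3 cycles of chemotherapy".

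On the length of treatment, section 2.3.1.1 states "Chemotherapy will be nominally three 3-week cycles administered over up to 12 weeks", and section 2.3.1.2 repeats this for the PROMIS outcome. Section 4.1 adds: "This time period may vary from subject to subject".

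Outcome 3 in section 2.3.1.2 is the change in PROMIS score from baseline to post-treatment. Section 10.4.2 rank-correlates pain reduction with SUVmax reduction. Section 10.7 requires that correlation to be at least 0.60, alongside the necrosis correlation, for the study to count as successful.

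**The concern.** A calendar week and an event-based time agree only when the event falls in that week. Here the event is the end of chemotherapy, which the protocol allows to slip by up to three weeks. When it slips, a coordinator who follows the week number collects the second form while the patient is still on treatment. A coordinator who follows section 4.1 or 9.3 waits. Both can point to the protocol, and no passage says which rule governs.

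At stake is whether the two variables in the secondary correlation describe the same interval. SUVmax change runs from baseline to a scan after chemotherapy. Pain change would run from baseline to Week 9. Six of the seven PROMIS items in Appendix B ask about the past 7 days (the other asks about pain right now), so a Week 9 form in a 12-week course mostly describes weeks 8 to 9. Current approval is for 5 subjects, so one mistimed pair is 1/5 = 20% of the data behind criterion 10.7(b).

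**Working it through.** **Inputs**

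- Nominal course: three cycles of 3 weeks; upper limit 12 weeks (2.3.1.1, 2.3.1.2).
- Second form: Week 9 on the literal reading of footnote c.
- Allowed window: 0 to 2 weeks before the scan (footnote c).
- Second scan: after chemotherapy, lag not stated (footnote a).

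**Assumptions**

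- Weeks are counted from the start of chemotherapy; the documents do not define the start.
- E is the week in which the stated course ends, from 9 to 12.
- L is the lag from that point to the scan. It is not given, so 0 and 1 week are shown.

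**Where Week 9 comes from.** 3 cycles × 3 weeks = 9 weeks. The stated week therefore reproduces as the nominal end of chemotherapy.

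**Formulas**

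- Scan week: S = E + L.
- Form before end of treatment by E − 9 weeks.
- Form before scan by S − 9 weeks.
- Permitted window: S − 2 to S. A Week 9 form is outside it when S − 9 > 2, that is, when S > 11.

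| E | L | Scan week S | Form before end of treatment (weeks) | Form before scan (weeks) | Window (weeks) | Week 9 form |
|---|---|---|---|---|---|---|
| 9 | 0 | 9 | 0 | 0 | 7–9 | inside |
| 9 | 1 | 10 | 0 | 1 | 8–10 | inside |
| 10 | 0 | 10 | 1 | 1 | 8–10 | inside |
| 10 | 1 | 11 | 1 | 2 | 9–11 | on the edge |
| 11 | 0 | 11 | 2 | 2 | 9–11 | on the edge |
| 11 | 1 | 12 | 2 | 3 | 10–12 | outside by 1 week |
| 12 | 0 | 12 | 3 | 3 | 10–12 | outside by 1 week |
| 12 | 1 | 13 | 3 | 4 | 11–13 | outside by 2 weeks |

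**Reading the table**

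- A 9-week course shows no conflict.
- Any course over 9 weeks puts a Week 9 form before the end of treatment.
- The 2-week window is breached only when the scan is after week 11. At the 12-week limit the gap is at least 12 − 9 = 3 weeks = 21 days, against 14 days allowed.

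**Does the 2-week window cure the problem by itself?** Not fully. It opens at S − 2 = E + L − 2, which is before E whenever L < 2 weeks. With E = 12 and L = 0 it opens at week 10, two weeks before treatment ends. Deleting the week number alone would still permit a form during treatment.

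**Sensitivity to the start of the count.** If weeks run from the baseline scan, which precedes chemotherapy, Week 9 falls earlier in treatment and the gaps widen. The documents also do not say whether chemotherapy ends at the last dose or at the close of the last cycle; the table uses the end of the stated course.

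**The case against.** The best defence is that Week 9 is only shorthand for the nominal end of treatment. It equals 3 × 3 weeks, the same sentence ties it to the second scan, and the next sentence gives a window counted from the scan, which the protocol history shows was a deliberate addition in version 4. The calendar puts the form in the Final Visit column, and section 4.1 places it at the Final Study Visit with no week number. A site that follows those texts takes the form at the final visit in every subject.

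Much of this stands. It rules out the stronger reading that the form is fixed at Week 9 for everyone, so that pain change covers 9 weeks in all subjects whatever their course. It also means that mistimed forms are possible, not certain. The documents do not say how many courses will run late.

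The defence does not remove the conflict. The calendar is the table that staff work from, its footnote names a week, and nothing says that the final-visit rule prevails when the two differ. The scan-based window does not settle it either, because it can open before chemotherapy ends.

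A reader might also infer that mistiming pulls the correlation toward zero and lowers the chance of reaching 0.60 by a calculable amount. The documents support neither step. An attenuation figure needs the correlation between Week 9 and end-of-treatment pain change and the share of subjects affected, and neither is given. The direction is open too: if delay is related to response or to pain, the bias could go either way.

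**Conclusion.** The inconsistency is real and limited. Followed literally, footnote c gives a pain score taken during treatment in any course over 9 weeks, by up to 3 weeks at the protocol's own 12-week limit. The form is also outside the footnote's 2-week window if the second scan is after week 11. Nominal 9-week courses are unaffected, as are sites that time the form by the Final Visit and complete it after chemotherapy ends.

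These figures rest on counting weeks from the start of chemotherapy and on taking the week number at face value. The textual conflict does not depend on the first of these.

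The consequence is confined to the secondary correlation in 10.4.2 and criterion 10.7(b), where the paired changes would cover different periods for the subjects concerned. The primary correlation with necrosis does not use the pain score. How far, and in which direction, the secondary correlation would move cannot be computed from the documents. The point is worth correcting because 10.7 requires both correlations to reach 0.60 and the correction costs little.

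**What to change.** 1. In footnote c, replace the Week 9 timing of the second form with: *at the Final Visit, after completion of neoadjuvant chemotherapy and before the 2nd scan*. This brings the footnote into line with sections 4.1 and 9.3.
2. State that, for the second form, the 2-week allowance applies only once chemotherapy is complete, and say what counts as complete for questionnaire timing.
3. Record the date of each form and each scan, with the date chemotherapy was completed, so that pairs outside the window can be flagged when the secondary correlation is reported.

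**Cost.** One reworded footnote, submitted as a modification for IRB and SRC approval under section 8.1, and a few date fields. No extra visit is needed, because the patient already attends for the second scan. The small downside is less flexibility in when the second form may be completed.
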